9.4.1.8 Unscheduled Safety Visit

If an SAE occurs in a subject, the subject will return to the site for a PK sample, as close as possible to SAE onset. Procedures and assessments are as follows:

1. Review concomitant medications.
2. A blood sample will be taken for PK analysis. The exact date and time of sampling must be documented.
3. Review the Drug Intake Diary for completion compliance and for the date and time of the last dose of study drug prior to the PK sample.
4. Perform physical and neurological examination and vital signs measurement (blood pressure, heart rate, respiration rate, weight and oral temperature). The neurological examination can be conducted \pm 1 day of the scheduled protocol visit. Complete TCNS in the course of the neurological examination, as well as NTSS-6 (with input from the caregiver) to ensure the subject did not develop new signs or symptoms of neuropathy.
5. Record AEs. AESIs (worsening of NFM [calculated as the average of the Screening visit and Baseline visit data] or prolongation of QTc) must be treated as SAEs and notified to ICON PV within 24 hours (see [Section 12.1.1](#)). ICON PV or ICON MM will then contact the study site to define follow-up activities and to assess whether the subject must be withdrawn from study.

9.5 Withdrawal of Subjects

Subjects may withdraw from the study at any time at their own request, or they may be withdrawn at any time at the discretion of the investigator or sponsor for safety, behavioural, or administrative reasons. The decision to withdraw consent and discontinue participation in the study will not prejudice the subject’s future medical treatment in any way. If a subject

does not return for a scheduled visit, every effort will be made to contact the subject. In any circumstance, every effort will be made to document subject outcome, if possible. The investigator should inquire about the reason for withdrawal, and request the subject to return for the EOT (Week 12) visit, if applicable, and follow-up with the subject regarding any unresolved AEs (for details see [Section 12.1.1.1](#)). The investigator or sub-investigator will be responsible for reporting subject withdrawal to Actinogen Medical/ICON. Subjects withdrawn from the study cannot be re-enrolled at a later time, regardless of the reason for withdrawal.

If a subject consents to undertake additional and optional study procedures/assessments but withdraws consent for doing so at a later visit, he/she will be retained in the study for the routine study procedures/assessments. If a subject withdraws from the study, and also withdraws consent for disclosure of future information, no additional data should be collected. Actinogen Medical/ICON may retain and continue to use any data collected before such withdrawal of consent.

Subjects shall be withdrawn during the course of the study when subject well-being is at risk, including but not limited to:

- Subject needs to take a prohibited medication. In case medication from the list of drugs potentially prolonging QTc (Appendix III) is introduced, the most appropriate approach will be discussed upfront with the ICON MM since the subject may not need to be withdrawn in all cases, e.g. in situations where the new drug is only provided temporarily, or in low doses, or in situations where baseline QTc was in the lower range of normal.
- ECG indicates a QTc level above a threshold of 480 msec at the Interim (Week 4 and Week 8) visits or an increase in QTc from Baseline > 60 msec (for details see [Section 12.3](#)). In this case, it should be reported as an AESI, within 24 hours.
- Subject develops signs or symptoms of peripheral neuropathy in any two tests of NFM, confirmed by the DSMB Nerve Function Monitoring sub-committee.
- The subject is unable to tolerate their prescribed study drug per protocol.
- Subject has evidence of drug-induced liver injury or any other drug-induced injury (such as thrombocytopenia), detected in ongoing safety monitoring of laboratory results.
- Subject is confirmed to be pregnant.

9.6 Early Termination

This study may be terminated prematurely at any time by Actinogen Medical for medical, operational or ethical reasons at individual or all study sites.

If the study is prematurely terminated or discontinued, Actinogen Medical/ICON will promptly notify the investigator, institutions and all competent regulatory authorities in writing outlining the reasons for the termination. The investigator or Actinogen Medical/ICON will promptly inform the Independent Ethics Committee/Independent Regulatory Board (IEC/IRB). After notification, the investigator must contact all

participating subjects and the hospital pharmacies (if applicable) within a reasonable time period and inform them of the premature termination/discontinuation of the study.

As directed by Actinogen Medical/ICON, all study materials, except documents needed for archiving requirements, will be collected and all eCRFs completed to the greatest extent possible. The study monitor will ensure that any outstanding data clarification issues and queries are resolved, and that all study records at the study site are complete.

10 TREATMENT OF SUBJECTS

10.1 Identity of Study Treatments

10.1.1 Administration of Study Treatments

One capsule of Xanamem™, or the matching placebo, will be administered orally with approximately 200 mL of preferably warm water QD, preferably with food in the morning, to eligible subjects from Baseline (Week 0) to EOT (Week 12) for a total of 12 weeks.

Subjects will attend the study site, in a fasted state, for a Baseline (Week 0) visit, Interim visits (Week 4 and Week 8) and EOT (Week 12) visit. Subjects should aim to take study drug at the same time each morning with food (30 minutes after the start of a standard meal) at the study site, and after all pre-dose blood samples have been taken.

Xanamem™ is formulated in green and cream-coloured size 3, Coni-Snap shaped gelatin capsules as an excipient blend at a dose of 10 mg (see Table 2). The dose of Xanamem™ will be 10 mg administered orally, QD.

Table 2 Ingredients of Xanamem™ and Matching Placebo Capsules, Using a Representative Dose of 10 mg (% w/w)

Component	Function	Placebo	10 mg
UE2343	Active pharmaceutical ingredient	0	5.26
Lactose	Diluent	95.0	89.74
Croscarmellose sodium	Disintegrant	4.0	4.00
Talc	Glidant	0.5	0.05
Magnesium stearate	Lubricant	0.5	0.05

Note: The formulations shown are based on % w/w with a nominal capsule fill weight of 190 mg.

10.2 Study Treatment Packaging and Labelling

10.2.1 Packaging

Xanamem™ will be provided in 35 mL high-density polyethylene bottles with child-resistant closure push down lids and an induction seal. Each bottle will contain 32 capsules and subjects will receive three bottles each (one bottle dispensed at the Baseline [Week 0] visit and one bottle dispensed at each of the Interim [Week 4 and Week 8] visits).

The drug product and matching placebo will be manufactured by Pharmaceutical Packaging Professionals Pty Ltd. All supplies will be provided in consistent packaging with consistent labelling to maintain the study blind. Further information relating to the study drug is available to the investigator(s) in the Investigator Brochure²⁰.

10.2.2 Labelling

Xanamem™ and placebo capsules will be packaged and labelled according to current ICH Good Manufacturing Practice and GCP guidelines and national legal requirements.

10.2.3 Shipment and Storage

The study drug will be supplied to study sites (initial and re-supply) by external providers on behalf of Actinogen Medical. The IWRS supports the study drug supply process. The recipient at the study site must check the study drug for completeness, correct bottle numbers, any loss or damage and confirm receipt. The study drug will be stored between 15 and 25°C (59 to 77°F), separately from normal hospital or practice inventories, in a locked facility with access limited to the investigator and authorised personnel. The investigator must ensure that the study drug is dispensed only to subjects enrolled in the study according to this study protocol.

Current stability data supports storage of the Xanamem™ and placebo capsules between 15 and 25°C (59 to 77°F). See drug label for further details.

10.2.4 Blinding and Randomisation of Study Treatment(s)

A double-blind design is employed so that both the investigators and the subjects will be unaware of the treatment assignment during the whole study.

After written informed consent is obtained from an eligible subject, a **6-digit subject number** will be assigned to this subject. The first digit will denote the country, followed by the study site number and a subject sequence number. This number will be created and allocated by the IWRS, when the subject first enters the system at Screening. The first subject screened at a study site will be assigned the number 001; the second will be assigned the number 002, and so on. For example, Subject 204001 will be the first subject screened at study Site 04 in Country 2. Subjects will be identified during the whole study only by their assigned subject number.

The randomisation codes will be computer-generated by ICON Biostatistics, and kept by a statistician independent from the project team. A copy will be provided to whomever performs the PK and PD assessments, when the PK and PD data are analysed, as well as to the DSMB. Randomisation codes will be generated in blocks stratified by site to ensure approximate balance between dose schemes (1:1) and balanced per site. Randomisation codes will be assigned sequentially as subjects become eligible for randomisation.

Subjects who are eligible for randomisation will be assigned a unique **3-digit randomisation number** at the Baseline (Week 0) visit by IWRS. This randomisation number identifies which treatment will be allocated to the subject. Subjects who withdraw after randomisation are not to be replaced and their randomisation number will not be re-used.

To ensure blinding, the study drug (Xanamem™ capsules) and the matching placebo have the same shape and size. Subjects will receive one capsule of Xanamem™ or one capsule of matching placebo capsule QD during the double-blind treatment period. Labels on the study drug containers will not identify treatment a subject is randomised to. Traceability of the treatment is ensured by the study drug number.

The **4-digit bottle number** will identify study drug packs and will be detailed on the study drug label.

Dispensing of study drug will be coordinated by IWRS. The system will assign a bottle number corresponding to the randomisation arm.

10.3 Procedure for Breaking the Randomisation Code

The study site investigator and appropriate ICON project team members will be authorised to access the Emergency Unblinding functionality within the IWRS. The system will require the user to enter an authorisation key number to complete the emergency unblinding transaction. The exact description of the treatment assigned to the individual subject then will be accessible. Emergency unblinding can thus be made for any subject without affecting the double-blind nature of the study. Subject treatment information may only be accessed in the event of an emergency and out of necessity to know the identity of the allocated study drug in order to institute appropriate therapeutic management.

Should a situation arise where unblinding is urgently required (i.e. knowledge of treatment code is required to adequately manage a life-threatening situation), the investigator at that study site may perform immediate unblinding through IWRS. If time allows, the investigator may contact the ICON MM prior to unblinding the individual subject to discuss the rationale for emergency unblinding.

In the event that emergency unblinding is performed, the investigator can view and must print the blinded confirmation document from IWRS. The investigator must record on the confirmation document printout the reason for the emergency unblinding, and sign the document. The confirmation document must then to be kept in a safe place until the end of the study. Once a randomisation code has been broken for a subject, he/she must be withdrawn from the study. The investigator must inform the ICON MM ([contact]) in writing within 24 hours.

10.4 Subject Compliance

After dispensing study drug (Xanamem™ or placebo) to subjects at Baseline (Week 0), investigators will follow up with subjects on their compliance to study drug. This first dose of study drug must be taken in the presence of the investigator/study site staff, to enable compliance and ensure the subject is capable to open the drug container and make an entry in the Drug Intake Diary.

Study drug accountability will be performed and documented by study site staff at the Interim visits (Week 4 and Week 8) and EOT (Week 12) visit. Subject compliance to treatment will be calculated as follows:

Treatment Compliance = (Number of study drug taken – number of study drug that should have been taken).

Any non-compliance will be documented, and explained in the source documents and the eCRF.

An 80% treatment compliance will still be acceptable as per protocol.

10.5 Study Treatment Accountability

Records will be maintained supporting the delivery of study drug(s) to the study sites, the inventory at the study sites, the use by each subject and the return to the study drug vendor or local on-site destruction.

These records will include dates, quantities, batch numbers, expiry dates and the unique code numbers assigned to the study drug and to the study subjects.

The investigator will be responsible for ensuring that the records adequately document that the subjects were provided the doses specified in the protocol and that all study drug received from the study drug vendor is reconciled. All study drug accountability records for study drug must be readily available for inspection by the study monitor and/or auditor, and open to regulatory inspection at any time.

10.6 Study Treatment Destruction

Any unused or partially used study drug or empty containers must not be destroyed until the study drug accountability documentation has been checked and specific permission for destruction has been given by the ICON study monitor. Any destruction of study drug must be documented and filed. Drug destruction may be performed on site, however, this must be discussed with the ICON study monitor before proceeding.

10.7 Concomitant Medications and Therapy

Medications that are considered necessary for the subject's safety and well-being may be given during the course of the study at the discretion of the investigator and must be recorded in the appropriate sections of the eCRF.

All medications taken by a subject within 1 month prior to Screening are regarded as **prior medication** and must be documented as such in the eCRF.

All medications still being taken by a subject at randomisation and which continue to be taken during the study are regarded as **concomitant medication** and must be documented as such in the eCRF.

10.8 Prohibited Medications

Details of prohibited medications are as follows (see Appendix III for a list of potential prohibited medications, including the brand names [please note this list is not exhaustive and serves as a guide to prohibited medications with brand names included and must be used in conjunction with the details of prohibited medications detailed below]):

- Initiating AChEIs or memantine during the study will not be permitted.
- Changes in medication or doses of psychotropics (or other medication that may have an impact on cognition such as anticholinergic medication) within 4 weeks prior to Screening and/or throughout the course of the study are not permitted.
- Regular intake of benzodiazepines may cause cognitive decline²⁴. Use of sedative drugs (specifically benzodiazepines, barbiturates and other anxiolytics) more than twice in a week or three times in a month in the past 6 months prior to Screening, or positive at

Screening will result in a subject being excluded from the study. The subject will be asked by site staff about their use of benzodiazepines. If the subject responds with “No use”, but subsequent benzodiazepine screening is positive, the subject will be excluded. If the subject responds with “Regularly”, the subject will be excluded. If the subject responds with “Only rarely” (i.e. maximum of twice a week), the site staff should enquire when the last dose of benzodiazepines had been taken. One urine benzodiazepine screening re-test will be allowed in cases where the subject’s intake of benzodiazepine is within the allowed dose and re-test is performed within 7 days of last benzodiazepine dose and prior to the Baseline visit. Positive re-test for urine benzodiazepines is exclusionary. If the re-test result is negative, the subject can remain in the study.

- Marked adrenal suppression occurs with high doses of inhaled corticosteroid above 1.5 mg/day (0.75 mg/day for fluticasone propionate)²⁵. Thus, inhaled glucocorticosteroids (e.g. prednisone equivalent) > 1 g per day, and any oral steroid preparations, are prohibited within 2 weeks prior to Baseline (Week 0) and/or throughout the course of the study.
- Several studies have shown the potential for hypothalamic-pituitary-adrenal axis suppression from potent topical corticosteroids²⁶. Thus, topical glucocorticosteroids > 50 g per week are prohibited during the study and within 2 weeks prior to Baseline (Week 0) and/or throughout the course of the study.
- Due to Xanamem™ being mainly metabolised by cytochrome P450 3A4 (CYP3A4), the following drugs which inhibit this isoenzyme must not be administered within 2 weeks prior to Baseline (Week 0) and/or throughout the course of the study: boceprevir, clarithromycin, erythromycin, indinavir, itraconazole, ketoconazole, nelfinavir, posaconazol, ritonavir, voriconazole, nefazodone.
- The following drugs strongly inducing CYP3A4 are prohibited within 2 weeks prior to Baseline (Week 0) and/or throughout the course of the study: carbamazepine, phenobarbital, phenytoin, primidone, rifampicin, St Johns Wort.
- Drugs known to prolong the QTc interval (including quinidine and nuedexta) may be provided with caution after the Screening visit. In case such medication is introduced, the most appropriate approach will be discussed upfront with the ICON MM since the subject may not need to be withdrawn in all cases, e.g. in situations where the new drug is only provided temporarily, or in low doses, or in situations where baseline QTc was in the lower range of normal.
- Vitamin B12 and Omega 3 (including specifically Souvenaid) are allowed if at stable doses for 3 months prior to Baseline.
- Drugs that are known to cause peripheral neuropathy are not permitted within 6 months prior to Screening and/or throughout the course of the study. Known drugs included:
 - Arsenic, colchicine and gold
 - Cardiovascular drugs: amiodarone, hydralazine, perhexiline

- Anti-cancer drugs: cisplatin, docetaxel, paclitaxel, suramin, vincristine
- Anti-infectives: chloroquine, isoniazid, metronidazole, nitrofurantoin, thalidomide
- Autoimmune disease drugs: etanercept, infliximab, leflunomide
- Dermatologicals: dapsone
- Anti-convulsants: phenytoin
- Anti-alcohol drugs: disulfiram
- Anti-human immunodeficiency virus (HIV) drugs: didanosine, stavudine, zalcitabine

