9.2.2 Risk/Benefit and Ethical Assessment

Xanamem™'s mechanism of action suggests a main role on hippocampal function, which may improve amnesic symptoms that are the main symptoms in subjects of mild AD. Furthermore, Xanamem™ may slow the progression of amyloid plaque deposition in the brain. Therefore, Xanamem™ has the potential for both symptomatic and disease-modifying effects in subject with mild AD.

Xanamem™ is an inhibitor of the 11β -HSD1 enzyme. Compounds which inhibit 11β -HSD1 are intended to affect the intracellular cortisone-cortisol balance, resulting in altered glucocorticoid action. It is therefore expected that AEs seen following the administration of Xanamem™ may be related to effects on glucose and fatty acid metabolism, or loss of suppression of innate immunity. In addition, inhibition of 11β -HSD1 results in enhanced cortisol clearance and potentially a compensatory increase in ACTH and cortisol secretion to maintain normal cortisol levels. As a result, ACTH-dependent secretion of adrenal androgens may be increased.

To date, Xanamem™ has an acceptable safety profile: in the MAD study²², all treatment-emergent AEs (TEAEs) were either mild or moderate in intensity. A total of 6/24 (25.0%) subjects reported at least one TEAE possibly related to study drug, whilst all the other TEAEs were reported as unrelated or unlikely to be related to study drug.

Of the five TEAEs considered to be moderate in intensity, one event of diarrhoea (20 mg UE2343) and one event of headache (35 mg UE2343) were considered as possibly related to study drug. The other moderate TEAEs were all unrelated or unlikely to be related to study drug. The laboratory parameters were within normal range and no clinically significant abnormalities were recorded. In the subsequent fed-fasted study²² in 12 subjects, the most commonly reported TEAE by preferred term was "Abnormal dreams", with a total of

five events reported by 5/12 (41.7%) subjects. These were considered possibly related to study drug (two events under fed conditions, one under fasted conditions and two across both the fed and fasted period), all mild in intensity and resolved.

Overall, there were no clinically significant abnormalities noted in nerve conduction studies for any of the subjects in the MAD cohorts.

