 - a) Inability to sense a stimulus even at the secondary (more proximal) skin area for pinprick, light touch, and vibration or temperature at the foot, in at least one extremity (in case neurography measures are normal, the case will be discussed with the ICON MM to assess subject eligibility)
 - b) Nerve conduction abnormalities beyond local normal values or inability to measure SNAP or CMAP in the primary or a secondary (back-up) nerve
 - c) NTSS-6 score > 6, but note that subjects are eligible even if they show:
 - Missing reflexes of the Achilles tendon (ankle), but a positive patellar (knee) tendon reflex
 - Missing ability to name toe or thumb position
6. Has had a stroke within the year prior to randomisation, as determined by the investigator.
7. Has a lifetime diagnosis of a major psychiatric disorder (other than dementia), based on the Diagnostic and Statistical Manual of Mental Disorders, 4th Edition criteria. This

- includes but is not limited to schizophrenia, schizoaffective disorder, bipolar affective disorder, alcohol dependence syndrome or major depressive disorder.
8. Has a history of disease directly related to the hypothalamus, the pituitary and/or the adrenal glands which affect the hypothalamic-pituitary-adrenal axis function.
 9. Has uncontrolled clinical conditions relating to glucose and lipid metabolism.
 10. Clinically significant ECG abnormalities, including QTc interval > 450 msec, following ECG tracings at Screening. A single repeat evaluation will be allowed if the investigator or designee has reason to believe the reading is faulty or to help assess the clinical significance of an abnormality. Any other ECG abnormality that is seen as exclusionary will first be discussed with the ICON MM.
 11. Use of any prohibited medication (see [Section 10.8](#) for details).
 12. Participation in another clinical study of an investigational drug or device whereby the last drug/device administration is within 60 days of Screening.
 13. Inability to communicate well with the investigator (i.e. language problem, non-fluent English [as scales will be provided in English only], poor mental development or impaired cerebral function).
 14. Subject will undergo the tests, ADAS-Cog v14, CDR-SOB, MMSE, NTB (executive domain) and RAVLT at the indicated time-points to avoid uncontrolled learning effects. Subjects who need to perform these tests externally to and in parallel with this study will be excluded.

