- **Optional PD assessment.** Samples for the determination of ACTH, DHEAS, androstenedione and testosterone will be taken from a sub-population of approximately 50 subjects enrolled into the main study, who also volunteer to take part in the PD sub-study, unless a higher number is defined as a result of the analysis of the data from those subjects, by the DSMB. Subjects who cannot provide a PK sample will not undergo PD sampling. Another attempt for PD sampling will be made at the next visit. The objective of this is to assess the impact of Xanamem™ on the hypothalamic-pituitary-adrenal axis. The sample must be taken pre-dose (as early as possible in the morning). For optimal results, the sample for androstenedione analysis

should be taken between 6 am and 10 am. PD results are blinded and will not be provided to the sites or the subjects; results will not be disclosed to study sites to avoid unintended subject treatment unblinding.

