Appendix III Prohibited Medication - Brand Names per Country

Appendix III Prohibited Medication

6 months prior to Screening (and throughout the study)

Sedative drugs (specifically benzodiazepines, barbiturates and other anxiolytics) more than twice in 1 week or 3 times in 1 month.

This also includes sedative (anticholinergic) anti-incontinence drugs:

Oxybutynin	Ditropan, Gelnique, Oxytrol, Cystrin, Kentera, Lyrinel, Oxytrol
probantheline/propantheline	Pro-Banthine
solifenacin	Vesicare, Vesomni
trospium	Sanctura, Flotros, Regurin, Uraplex

Sedative (and anticholinergic) Antihistamines:

chlorpheniramine/chlorphenamine maleate	Chlor-trimeton, Efidac, Kloromin, Phenetron, Teldrin, Piriton
cyproheptadine	Periactin
diphenhydramine	Benadryl, Beldin, Belix, Benylin, Nytol
hydroxyzine	Atarax, Vistaril, Orgatrx, Ucerax

Sedative (anticholinergic) antidepressants are not allowed at any dose. NOTE: Major Depression is an Exclusion criterion:

Amitriptyline, amoxapine, clomipramine, desipramine, doxepin, imipramine, nortriptyline, paroxetine

Medicines that are known to cause peripheral neuropathy:

	Arsenic , Colchicine, Gold
Cardiovascular drugs	Amiodarone, Hydralazine, Perhexiline
Anti-cancer drugs	Cisplatin, Docetaxel, Paclitaxel, Suramin, Vincristine
Anti-infectives	Chloroquine, Isoniazid, Metronidazole, Nitrofurantoin, Thalidomide
Anti-human immunodeficiency virus (HIV) drugs	Didanosine, Stavudine, Zalcitabine
Autoimmune disease drugs	Etanercept, Infliximab, Leflunomide
Dermatologicals	Dapsone
Anti-convulsants	Phenytoin
Anti-alcohol drugs	Disulfiram

4 weeks prior to Screening

Changes in medication or doses of psychotropics (antidementive drugs)

2 weeks prior to Baseline (and throughout the study)

Inhaled glucocorticosteroids (e.g. prednisone equivalent) > 1 g per day, topical glucocorticosteroids > 50 g per week, and any oral steroid preparations

Inhaled glucocorticosteroids

budesonide	Budelin, Easyhaler, Pulmicort, Symbicort
flunisolide	Aerobid, Aerospan
fluticasone	Advair, Flovent, Flixotide, Seretide, Breo Ellipta
ciclesonide	Alvesco
mometasone	Asmanex
beclomethasone	Beclovent, Qvar, Fostair, Vanceril

Topical glucocorticosteroids

Hydrocortisone	Dermacort, Epicort, Egocort, Sigmacort
Triamcinolone	Kenacort
Fluticasone	Cutivate
Clobetasol	Dermovate, Clobex, ClobaDerm, Temovate
Betamethasone	Betnovate, Diprosone, Diprolene, Celestone
Halobetasol	Ultravate

Drugs known to inhibit or induce CYP3A4 as listed below:

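### The inhaled-corticosteroid limit of 1 g per day is nominally about 670 times the dose that the protocol gives as its reason, so it excludes none of the users it was written for

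*Protocol*

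**What the plan says.** The inhaled-steroid bullet in Protocol 10.8 opens with its reason: "Marked adrenal suppression occurs with high doses of inhaled corticosteroid above 1.5 mg/day (0.75 mg/day for fluticasone propionate". The next sentence, introduced as a consequence, prohibits "inhaled glucocorticosteroids (e.g. prednisone equivalent) > 1 g per day" from two weeks before Baseline and throughout the study. The same sentence bans oral steroids at any dose. Topical steroids have their own limit in the bullet that follows.

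Appendix III restates the rule as "Inhaled glucocorticosteroids (e.g. prednisone equivalent) > 1 g per day, topical glucocorticosteroids > 50 g per week, and any oral steroid preparations" and then lists inhaled products. Its fluticasone row reads "Advair, Flovent, Flixotide, Seretide, Breo Ellipta". Section 10.8 says that this appendix is a guide to be read together with the section's own text, so the list does not ban those brands regardless of dose.

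Two operative rules depend on the figure. Exclusion criterion 11 (Protocol 9.3.2) is "Use of any prohibited medication", with a reference back to 10.8. Protocol 9.5 lists among the grounds for withdrawal "Subject needs to take a prohibited medication".

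On the biology, Protocol 9.2.2 expects the drug to enhance cortisol clearance, with "potentially a compensatory increase in ACTH and cortisol secretion to maintain normal cortisol levels". Protocol 13 sets up the optional pharmacodynamic assessment: "Samples for the determination of ACTH, DHEAS, androstenedione and testosterone will be taken from a sub-population of approximately 50 subjects". Its purpose is to assess the drug's effect on the hypothalamic-pituitary-adrenal (HPA) axis. Cortisol is measured separately, in the PK blood samples.

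**The concern.** The reason is stated in milligrams and the limit in grams. If the reason is right, the limit cannot do its job: every subject between the cited suppression level and 1 g per day is admitted. No other rule catches them. Exclusion criterion 8 covers disease of the hypothalamus, pituitary or adrenals, not inhaled steroid use, and the oral and topical rules cover other routes.

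Two things are at stake. The first is safety. The protocol judged inhaled-steroid adrenal suppression important enough to restrict, in a trial of a drug that acts on cortisol metabolism, and the restriction as written is empty. The second is the precision of the HPA-axis data. Adrenal suppression from another source adds variability to ACTH, DHEAS, androstenedione, testosterone and cortisol. With 1:1 randomisation the expected result is noise rather than confounding. Change-from-baseline summaries help with stable users, but not with a subject who starts or increases inhaled steroid after Baseline, which the limit also permits.

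**Working it through.** **Inputs from the documents**
- Level cited for marked suppression: 1.5 mg/day inhaled; 0.75 mg/day for fluticasone propionate (Protocol 10.8).
- Operative limit: 1 g/day = 1000 mg/day (Protocol 10.8 and Appendix III).
- Pharmacodynamic sub-study: about 50 subjects (Protocol 13); randomisation 1:1.

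**Does the limit follow from the reason?** Gap = limit / cited level.
- General: 1000 / 1.5 = 666.7.
- Fluticasone propionate: 1000 / 0.75 = 1333.3.

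The stated limit cannot be reproduced from the stated reason.

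**Does the prednisone-equivalent label close the gap?** Let k be the mg of prednisone equivalent to 1 mg inhaled. The documents give no k, so the values below are assumptions. Gap = 1000 / (cited level × k).

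| Assumed k | 1.5 mg/day in prednisone equivalent | Gap | 0.75 mg/day in prednisone equivalent | Gap |
|---|---|---|---|---|
| 1 | 1.5 mg | 666.7 | 0.75 mg | 1333.3 |
| 10 | 15 mg | 66.7 | 7.5 mg | 133.3 |
| 50 | 75 mg | 13.3 | 37.5 mg | 26.7 |
| 100 | 150 mg | 6.7 | 75 mg | 13.3 |

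For the gap to vanish, k must be 1000 / 1.5 = 667, or 1000 / 0.75 = 1,333 for fluticasone propionate. Nowhere in the assumed range of 1 to 100 does the limit reach a subject at the cited level.

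**Would reading g as mg repair it?** A limit of 1 mg/day is 1 / 1.5 = 0.67 of the general level, so it is stricter there. It is 1 / 0.75 = 1.33 times the fluticasone propionate level, so users above 0.75 and up to 1 mg/day would still pass. Appendix III has a fluticasone row but does not say which products are the propionate.

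**Weight of one affected subject in the sub-study.** Assuming volunteers split 1:1, there are 50 / 2 = 25 per arm. One subject is 1 / 25 = 4% of an arm. Over an assumed 0 to 3 per arm, the share is 0 to 3 / 25 = 12%.

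**The case against.** The strongest reply concedes the mismatch and disputes its consequence.

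- **The factor of 667 does not compare like with like.** The reason is in mg of inhaled drug and the limit in prednisone equivalent. This stands as a caveat on size, which is why the factor is called nominal. It does not rescue the limit, because the conversion required is far outside the assumed range.
- **Other safeguards exist.** The investigator must judge the subject to be in good health, and a medical examiner must be satisfied of fitness. Orthostatic vital signs and safety biochemistry are scheduled through the study. The DSMB sees unblinded safety and pharmacodynamic data. A prescriber reading the bullet also sees the mg/day levels in the preceding sentence. All of this lowers the practical risk, but none of it sets an inhaled-dose limit.
- **The risk to inhaled-steroid users is inferred.** Protocol 9.2.2 describes only a potential compensatory rise in ACTH and cortisol secretion and does not mention such users. That is fair. The safety point rests on the protocol's own decision to restrict them, not on a demonstrated hazard.
- **The analytic effect is small.** The pharmacodynamic sub-study is optional, SAP 7.9 specifies summaries and no hypothesis test for these parameters, and there may be no affected subject. This stands, and it bounds the importance of the point.
- **The remedy depends on data not shown.** Protocol 10.7 and SAP 7.5 require medications to be recorded and listed but do not say that dose is captured, and the post-lock plan named in SAP 7.12 is a separate document. Both points stand as conditions on the fix.

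**Conclusion.** The concern holds. The inhaled limit contradicts its own rationale by a nominal 667-fold, or 1,333-fold for fluticasone propionate. It remains at least 6.7-fold too high (13.3-fold for fluticasone propionate) over assumed conversions of 1 to 100 mg prednisone per inhaled mg. The error appears in both places where the limit is stated, and eligibility and withdrawal both rest on it, so it is more than clerical. A slip of g for mg is plausible but cannot be proved from the documents.

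The finding is confined to the inhaled part of the rule. Sample size, type I error and the primary endpoints are not affected. For the pharmacodynamic and cortisol data the expected harm is added variability. Its amount depends on how many subjects inhaled more than the cited levels, which the documents do not give and which could be none. It should be fixed.

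**What to change.** **Text.** In Protocol 10.8 and Appendix III, replace the prednisone-equivalent gram limit with an inhaled-dose limit no higher than the protocol's own cited levels: more than 1.5 mg per day, or more than 0.75 mg per day for fluticasone propionate. The medical team should confirm value and unit, since the intended basis of the limit is not documented.

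**Analysis.** From the recorded concomitant medications, list subjects whose inhaled dose exceeded those levels. Repeat the SAP 7.9 summaries of ACTH, DHEAS, androstenedione and testosterone without them as a sensitivity check, and write the same check for cortisol into the post-lock plan referred to in SAP 7.12. If the listing is empty, the report can say so. Do not reclassify these subjects as protocol violators or remove them from the per-protocol set, because they complied with the limit in force.

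**Cost.** A one-line change in two places, one listing and one repeated set of summaries. Under a corrected limit a few otherwise eligible inhaled-steroid users would be excluded. On the planned dates (last visit February 2019; SAP dated 25 March 2019) the text change comes too late to affect enrolment, so the sensitivity summary is the step that still helps. It requires that inhaled dose was recorded along with the medication.
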